### *Psychological health*

[figure not shown]

Figure 3: sagittal view of the Q-Force.

A	Back support	E	Inclinometer
B	Sitting area	F	Force transducer
C	Leg socket	G	Length transducer
D	Pedestal		

Depression is measured using the Patient Health Questionnaire Nine (PHQ-9). It includes nine items, which are the nine symptoms of depression according to the DSM-4. A PHQ-9 score >10 has a sensitivity of 88% and a specificity of 88% for major depression. The test-retest reliability is excellent (ICC correlation = 0.81-0.96) and is a responsive depression outcome measure in older adults. Most patients are able to complete the Patient Health Questionnaires in several minutes with no assistance. Major depression is diagnosed if 5 or more of the 9 depressive symptom criteria have been present at least "more than half the days" in the past 2 weeks and 1 of the symptoms is depressed mood or anhedonia. Other depression is diagnosed if 2, 3, or 4 depressive symptoms have been present at least "more than half the days" in the past weeks, and 1 of the symptoms is depressed mood or anhedonia. The level of depression severity can be measured by adding together the item scores (score 0 for 'not at all', score 1 for 'several days', 2 for 'more than half the days', and 3 for 'nearly every day'). Löwe and colleagues (2004) conclude that a PHQ-9 change score of 5 or greater reflects a clinically relevant change.

To assess the presence of general anxiety the Generalized Anxiety Disorder- 7 item scale (GAD-7) is used. This questionnaire is based on the DSM- IV criteria and it can be self-administered. The questionnaire has a good internal consistency (Cronbach- $\alpha$  =0.92) and test-retest reliability (ICC= 0.83). The score of all seven items range from 0 (Not at all) to 3 (Nearly every day). The total score is the sum score of the seven items (range 0 to 21). The total score is categorized in to four severity groups: minimal/no anxiety (0-4), mild (5-9), moderate (10-14), or severe (15-21). The optimum cut-off value of GAD at 10 points has shown a sensitivity of 89% and a specificity of 82%.

Quality of life will be assessed with the RAND-36 version 2. This validated questionnaire with a good reliability includes nine health domains: physical functioning, social functioning, role limitations due to physical health problems, role limitations due to emotional functioning, mental health, vitality, pain, general health, and perceived health change. Outcomes at each dimension will be defined on a scale between 0 and 100; a higher score means a better health. The questionnaire is part of the routine preoperative assessment.

#### *Economic evaluation*

The iMTA Productivity Cost Questionnaire (PCQ) will be used to measure productivity losses of paid work and unpaid work. The PCQ is a generic instrument developed to quantify health-related productivity losses for use in economic evaluations. It is largely based on previously available instruments and builds on the current scientific state of play in productivity cost measurement and valuation.

Health-care utilization will be measured by using the iMTA Medical Cost Questionnaire (MCQ) at baseline and after 3-4, 7-8 and 12 months of follow-up. The MCQ is a generic instrument for measuring medical costs. The MCQ includes questions related to frequently occurring contacts with health care providers. To improve the feasibility and reliability, both recently developed questionnaires (PCQ and MCQ) were 'translated' into simple language by a specialized agency. Additionally, a feasibility study was performed to assess the comprehensibility of the questions in practice.

The EQ-5D-5L will be used to estimate the quality-adjusted life years (QALY's). A QALY is a measure of the state of health of a person or group in which the benefits, in terms of length of life, are adjusted to reflect the quality of life. One QALY is equal to 1 year of life in perfect health. QALYs are calculated by estimating the years of life remaining for a patient following a particular treatment or intervention and weighting each year with a quality-of-life score (on a 0 to 1 scale). It is often measured in terms of the person's ability to carry out the activities of daily life, and freedom from pain and mental disturbance.

The EQ-5D-5L is a standardized and validated instrument for describing and valuing health-related quality of life developed by the EuroQol Group to provide a simple, generic measure of health for clinical and economic evaluation. The EQ-5D consists of two elements. The first element is a descriptive system including five dimensions: mobility, self-care, usual activities, pain & discomfort and anxiety & depression. The respondent is required to rate his own health on these five dimensions. Each dimension has five levels: no problems, some problems, moderate problems, severe problems and extreme problems/unable to. The second element is a rating of the respondent's own current health state on a vertical, visual analogue scale where the endpoints are labeled 'Worst imaginable health state' (0 points) and 'Best imaginable health state' (10 points).. Utility values for the EQ-5D-5L will be calculated based on the new Dutch tariff.

### *Lifestyle risk factors,*

Physical activity is assessed using the Sensewear GECKO mini-armband (SWA) and the long version (27 questions) of the International Physical Activity Questionnaire (iPAQ). The SWA is worn on the upper arm and collects a variety of physiologic data through multiple sensors (a three-axis accelerometer, heat flux sensor, near-body ambient temperature sensor, and galvanic skin response sensor) to give a profile of physical activity. The reliability and validity is investigated in different studies

The iPAQ assesses physical activity undertaken in the prior 7 days, across 4 subcategories: (1) job-related physical activity; (2) transportation-related physical activity; (3) housework, house maintenance, and caring for family and (4) recreation, sports. In addition it includes a category about sedentary activity. Per category, the patient is asked to report the frequency (days per week) and duration (time usually spent per day) of moderate-intensity physical activity, vigorous-intensity physical activity, walking activities, bicycling, and time spent sitting. The iPAQ questionnaire has a good test-retest reliability (Spearman's rho of 0.8). Criterion validity of the self-report iPAQ against a CSA accelerometer is moderate (Spearman's rho of 0.3), which is comparable to most other self-reported physical activity questionnaires. From the data MET-minutes/ week can be calculated by weighting each type of activity by its energy requirements. There are three levels of physical activity (low, moderate and high) to classify the groups. Smoking behavior and history will be assessed with five questions.

### *Potential mediators*

Illness perception is measured with the validated revised illness perception questionnaire (IPQ-R), which is based on the Leventhal's Self-Regulatory Model. The questionnaire contains the following dimensions: identity, timeline, consequences, personal control, treatment cure control, illness coherence, emotional representation, and causes. The dimensions of IPQ-R showed a test-retest reliability with correlations ranging from 0.46 to 0.88. In patients with myocardial infarction a good internal consistency was shown (alpha = 0.73 to 0.94). For this study the subscales personal control, treatment control, and consequences are included. These scales are chosen because of their contribution to psychological distress.

The cardiac self-efficacy scale (CSA) was developed by Sullivan and colleagues (1998) to measure self-efficacy in addressing the challenges posed by coronary disease. Patients are asked 16 items to rate: 'how confident are you that you know or can...' on a five-point Likert scale (0= not at all, 1= somewhat confident, 2 = moderately confident, 3 = very confident, 4 = completely confident). The scale has demonstrated a high internal consistency (Chronbach's alpha = 0.87-0.90). In addition, the scale has shown good convergent and discriminant validity in relation to outcomes as quality of life, functional status and anxiety.

Table 4: Overview and time indication of the primary and secondary outcomes.

		T1	T2	T3	T4	T5	T6	T7
	Duration (min)	Accepted for CS	-8 to -1 Day	H	4-7 days	3-4 months	7-8 months	1 year
Procedures								
Sign informed consent	45	X						
Check in/exclusion criteria		X						
Medical history		X						
Demographics		X						
Composite weighted outcome		*			X		*	
Functional status		X		X				
Postoperative surgical complications		X		X				
Hospital readmissions 		X		X				
Major adverse cardiac events		X		X				X
Secondary outcomes								
Events and complications								
Atrial fibrillation				X				
PICU				X				
Physical capacity								
6MWT	25	#	#	#	X			X
Muscle strength	20	X	X	X	X			X
Functional status (KATZ)	5	*		X	X			X
Psychological health								
Depression (PHQ-9)	5	*	X	X				*
General anxiety (GAD)	5	*	X	X				*
Quality of life (Rand-36 V2 & EQ-5D-5L)	12	*		X	X			*
Economic evaluation								
Health care use (MCQ)	15	X		X	X			X
Work participation (PCQ)	10	X		X	X			X
Lifestyle risk factors								
Physical activity (iPAQ/ Sense Wear)	10	X		X	X			X
Smoking behavior	5	X		X	X			X
Potential mediators								
Illness representations (IPQ-R)	5	X	X	X				X
Self-efficacy (CSA)	5	X	X	X				X
Standard care (min)		52						22
Study patients (min)		117	63					102
				45	124	25		

 Only all-cause mortality;  Start screening at 30 days after surgery; \* Measured in standard care; X measures added for study patients, but are standard care if patient is randomized to pre- and postoperative CR; CS: Cardiac surgery; H: the period between the surgery and when patient meets discharge criteria; PICU: prolonged stay at intensive care unit; 6MWT: six minutes walking test;

### 7.1.2 Other study parameters (if applicable)

Other study parameters, to routinely collected measures, include:

- Baseline characteristics (such as age, gender, weight, length, wrist/hip ratio, marital status, living situation, education level, occupation, medical history, co morbidities, anxiety for surgery, waiting time)
- Surgery parameters that may influence primary and secondary study parameters (such as type of surgery, use of cardiopulmonary bypass, surgery duration, cross-clamp time, use of internal mammary graft)
- Results of routinely collected blood tests and hospital stay
- Performed training load (duration, type, frequency and intensity) during the CR program
- Compliance to the CR programs, referred hospital and travel distance to rehabilitation center (this may influence the compliance of the CR program).

### 7.2 Randomisation, blinding and treatment allocation

Patients are randomly assigned to one of two CR programs in a 1:1 ratio. Allocation to the PRE+POST group or POST group will occur after baseline measurements. Blocked randomization is used to ensure continued inclusion rates in both CR programs.

Randomization is stratified for type of surgery (CABG, AVR, AVR+CABG and other), gender and age ( $\geq 65$  years and  $< 65$  years). Medical staff and researchers are not blinded, because of the complex logistics of the PRE+POST CR program.

### 7.3 Study procedures

#### Inclusion into the study

##### *Elective patients (waiting period > 5 weeks)*

After informing the patients about the surgery the cardiologist checks the inclusion criteria. All eligible patients are informed about the study. If patients express an interest in study participation a patient information letter and informed consent is provided (attachment E1). The researcher will screen the patient for exclusion criteria and asks the patient to give informed consent during routinely preoperative examination. The maximum time between the appointment with the cardiologist and preoperative examination is 14 days; during this period the patient has time for reflection. There will be sufficient time for questions during the meeting with the researcher. In addition, patients are informed that they can withdraw from the study at any time without consequences. The measurements of T1 are performed if the patient meets the study criteria and informed consent is signed. Random allocation is performed after T1 measurements.

Patients who do not want to participate are asked to give written consent (attachment E1.2) for using data, which are collected during routine care. Patients are asked for this Heart-ROCQ study registry to get insight in the possible bias of the included population and thus the generalizability of the results of the study. Data are not used for the primary statistical analyses.

**Baseline measurement (T1)**

Rand-36, KATZ, PHQ-9, GAD and the additional questions about smoking are part of the standard care protocol before surgery using an online questionnaire. The physical tests (6MWT and strength tests) are performed and the MCQ, PCQ, EQ-5D-5L, iPAQ, IPQ-R, CSA questionnaires will be provided to the patients when they sign informed consent for participating in the study. In addition, patients are asked to wear the Sense Wear mini-armband (SWA) for one week. They will be asked to return the questionnaires and the SWA before the preoperative consultation (approximately one week later).

**Week before surgery (T2) and hospitalization (T3)**

Eight days prior to surgery the PHQ-9, GAD, IPQ-R and CSA are provided. Patients are asked to fill in the questionnaires preceding two days before surgery. In standard care patients are admitted to hospital one day before surgery. During this day physical capacity measurements (6MWT and muscle strength) are performed by a researcher, research assistant or physical therapist. These measurements are also performed on day four to seven after surgery (or when the drain is not removed, after the drain is removed).

**Three-four months post-surgery (T4)**

Approximately 3-4 months postoperatively, patients will be seen by a researcher at the outpatient clinic in the UMCG. During this visit, physical capacity will be tested (muscle strength and 6MWT). One to two weeks before the appointment, the questionnaires (Rand-36\_v2, KATZ, PHQ-9, GAD, MCQ, PCQ, EQ-5D-5L, iPAQ, smoking behavior, CSA) are sent to the patients and the patients are asked to fill these in before the appointment. In addition, the SWA is sent to the patients with the question to wear this activity monitor one week prior to the appointment. During the measurement the questions according the primary endpoint are asked.

**Seven to eight months after surgery (T5)**

Seven to eight months after surgery patients will be interviewed by telephone about their health care use (MCQ), work participation (PCQ) and EQ-5D-5L during the last four months. Research-assistants will perform the interviews.

**One year after surgery (T6)**

Patients are followed-up by a researcher-(assistant) at the outpatient clinic, during the yearly control appointment of the cardiologist (one year after surgery). During this visit, physical capacity will be tested (muscle strength and 6MWT). Rand-36, PHQ-9 and GAD are part of the standard care protocol one year after surgery using an online questionnaire. As in T4, the questionnaires (KATZ, MCQ, PCQ, EQ-5D-5L, iPAQ, smoking behavior and CSA) and SWA are sent to the patients prior to the measurement. During the measurement the questions according the primary endpoint are asked.

***Procedure of primary outcome***

Postoperative complications are routinely collected in standard care. These parameters will therefore be derived from medical record and hospital database. At T4 and T6 (3-4 months and one year follow up) patients are asked if they were hospitalized, underwent any cardiothoracic surgical intervention or any percutaneous interventions since the surgery. In addition, they will be asked if they had a myocardial infarction or CVA. The researcher will check documentation at the hospital in which the intervention or treatment was performed, if

patients have had one of these major adverse cardiac events. The rate of mortality will be checked in the municipal administration. The cause of death is reviewed by interrogation of the general practitioner, if patient has died outside of the hospital.

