## SUMMARY

**Rationale:** Patients undergoing cardiac surgery are at risk of developing perioperative complications and major adverse cardiac events, mainly related to both their preoperative status and type of surgical procedure. Postoperative exercise based cardiac rehabilitation (CR) is an effective therapy to prolong survival and improve quality of life. However, little is known about the effect on post-operative complications, quality of life and return to work of a combined pre- and post-operative CR program encompassing physical therapy, dietary counseling, psychological support and life style management compared to a CR program, which is provided only after cardiac surgery.

**Objective:** to determine whether a pre- and postoperative (PRE+POST) CR program improves the short (up to three months) and long term outcomes (up to one year) of the cardiac surgery (i.e. reduction in postoperative surgical complications, readmissions to hospital and major adverse cardiac events in conjunction with improvements in the physical component of health related quality of life), when compared to postoperative CR only (POST).

**Study design:** A Prospective Randomized Open controlled trial, Blinded End-point. Patients are randomized between two standard care CR programs. One group will start a POST CR program after surgery. The other group will be randomized to a combined PRE+POST CR program.

**Study population:** Patients (age > 18 years) admitted for elective coronary bypass surgery, valve surgery and/or aortic surgery

**Main study parameters/endpoints:** The primary outcome is a composite weighted endpoint of postoperative surgical complications, re-admissions to hospital, major adverse cardiac events and health related quality of life (two domains: physical functioning and physical problem), at three months and one year after surgery. Endpoints are determined by an independent endpoint committee, blinded to the group allocation. Secondary, the study focuses on physical health (cardiorespiratory fitness, muscle strength and functional status), psychological health (feelings of anxiety and depression), work participation, economics, lifestyle risk factors (physical activity and smoking behavior), self-efficacy and illness representations.

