### 1.1 OBJECTIVES

The primary aim of this study is to determine the effectiveness of a pre- and post-operative (PRE+POST) cardiac rehabilitation program compared to a phase II cardiac rehabilitation program that is provided only post-operative (POST), three months and one year after elective cardiac surgery. The effectiveness is primary measured with a composite endpoint of two subdomains of health related quality of life (physical functioning and physical problem), surgical complications, readmissions to hospital and major adverse cardiac events). The preoperative phase of the PRE+POST CR program consists of a outpatient CR program and the postoperative phase of an in- and outpatient phase. The postoperative phase of the POST CR program consists of an outpatient phase.

Secondary, this study is designed to evaluate the effect of the CR programs on:

- Prolonged stay at the intensive care, the occurrence atrial fibrillation and re-thoracotomies (*Complications and events*)
- Cardiorespiratory fitness, muscle strength and functional status (*Physical health*)
- Feelings of anxiety, depression and quality of life (*Psychological health*)
- Work participation
- Economic evaluation: health care costs and work-related costs
- Physical activity and smoking consumption (*Lifestyle risk factors*)
- self-efficacy and illness representations (*Potential mediators*)

The hypotheses are that patients who follow the PRE+POST CR program will benefit in terms of improved preoperative status, self-efficacy and illness perceptions compared to POST patients who follow postoperative CR only. In addition, PRE+POST patients may adopt a healthier lifestyle compared to patients who follow a POST CR program. This may prevent postoperative surgical complications, readmissions to hospital and major adverse cardiac events in conjunction with improvements health related quality of life, physical and psychological health. Furthermore, we expect that the PRE+POST CR program will be cost-effective in terms of a reduced health care use and an earlier return to work after cardiac surgery.

[figure not shown]

Figure 1: Intervention components, potential mediators and outcomes of the Heart-ROCQ study.

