## 2. STUDY DESIGN

This prospective randomized open controlled trial (Figure 2) is executed in cardiac patients undergoing a thoracic surgery procedure in a single center (UMCG). Double blinding (researcher and participants) is not possible because of logistic reasons. However, the primary endpoint is evaluated by an independent end-point committee, blinded for group allocation.

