***Measurements of physical tests and questionnaires***

Patients will be asked to fill in short questionnaires and perform physical tests at six measurement time points (Figure 2). The first measurement is conducted when patients are admitted for the surgery (T1). The second measurement is one day before surgery (T2). The third measurement is four to seven days after surgery (or when the drain has been taken out and patient is able to walk (whichever of the two is last, T3). The fourth measurement is three to four months after surgery (T4), the fifth measurement is seven to eight months after surgery (T5) and the sixth one year after surgery (T6).

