***Screening outcomes***

Prolonged mechanical ventilation, delirium, lung infection, atrial fibrillation and readmissions and prolonged stay at the intensive care are measured in the period between surgery and when patient meets the UMCG discharge criteria.

The UMCG discharge criteria are:

- 1) no drain, no external pacemaker lead, no infusion or oxygen present,
- 2) stable clinical conditions (stable lab results, X-ray and haemodynamic parameters),
- 3) Able to perform basic ADL-activities (i.e. going independently to the toilet).

Hospital admissions are screened in period between 30 days after surgery and one year after surgery. Deep wound infections and re-thoracotomies are screened up to 120 days after surgery. Surgical and percutaneous interventions, myocardial infarction and CVA are screened up to one year after surgery. All-cause mortality is screened up to five years after surgery.

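### The primary score has no rule for major events between randomisation and surgery, or for patients never operated, although the arms already differ in that interval

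*Combined protocol and SAP*

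**What the plan says.** **Allocation and treatment.** Section 7.3 places random allocation after the T1 measurements, before the operation. Section 4 gives the PRE+POST arm training three times a week for 4-6 weeks before surgery. Table 1 shows that the POST arm waits at home without support.

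**Time origin of the score.** Section 1.1 sets the objective at "three months and one year after elective cardiac surgery", and the main endpoint in section 7.1.1 uses the same two times.

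**Event ascertainment.** Under the procedure for the primary outcome in section 7.3, patients are asked at T4 and T6 whether they were hospitalised or "underwent any cardiothoracic surgical intervention or any percutaneous interventions since the surgery". The next sentence reads "In addition, they will be asked if they had a myocardial infarction or CVA", with no start date.

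**Windows.** Section 2 states "Surgical and percutaneous interventions, myocardial infarction and CVA are screened up to one year after surgery" and follows mortality to five years. Both are upper limits. Table 2 gives death 3 points, and infarction and stroke 2 points each, again without a start. The in-hospital complications and the readmissions do have starts: the operation and day 30 respectively.

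**Who decides, and who is analysed.** Section 2 says "the primary endpoint is evaluated by an independent end-point committee, blinded for group allocation", but no readable text tells the committee where the window begins. Intention to treat is stated in section 2, in the cross-over text of section 4 and in section 9.2. Section 9.1 fills missing quality of life with the worst case. Section 9.2 leaves other missing-data methods until the data have been studied.

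Figure 2 is not shown and Table 4 is broken in the text available, so I rely on neither, apart from the Table 4 footnote that starts readmission screening at day 30.

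**The concern.** The preoperative wait is the interval in which one arm is treated and the other is not. The introduction argues that waiting may raise risk and that the time can be used to improve the patient's condition. An effect of the programme, in either direction, could therefore appear before the operation: as a death, an infarction, a stroke, an unplanned intervention, or an operation that never takes place.

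The questions and visits are dated from the operation. If they are followed as written, some of these events fall outside the score. A patient who never reaches surgery has no T4 or T6 date at all. If such patients drop out of the primary analysis, the comparison is among those who reached surgery, a post-randomisation condition that treatment may affect. The trial is open-label, so a rule chosen after such cases are seen would also be open to criticism.

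**Working it through.** **1. Does any other provision close the gap?**

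| Provision | What it covers | Preoperative event or non-operation? |
|---|---|---|
| Section 4, cross-overs | Referral to another rehabilitation programme | No |
| 7.5 | No replacement of withdrawn patients | No score given |
| 7.6 | Stopping rehabilitation, missed visits | Refers to the study schedule, whose follow-up visits are dated from surgery |
| 8.2.2 | AEs and SAEs asked at T2 | Collected, but not linked to the score |
| 9.1 | Missing quality of life | Two components only |
| 9.2 | Other missing data | Left open |

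None does.

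**2. The plan's own figure.** Inputs from section 3.4: mean 1.0, SD 0.9, difference 0.3, alpha 0.05, 80% power; two-sided per section 9.2. A two-sample t-test needs 142.2 per arm, rounded up to 143, as stated. Power at 143 is 80.2%. The sample size is not in error. The planned 350 gives 175 per arm.

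**3. What one case is worth** (175 per arm, usual score 1.0)
- Preoperative death scored 3 rather than omitted: (3 - 1)/175 = 0.0114, or 3.8% of 0.3.
- The same death with both worst-case quality-of-life points (3 + 1 + 1 = 5): (5 - 1)/175 = 0.0229, or 7.6%.
- Preoperative infarction or stroke counted rather than not, patient kept: 2/175 = 0.0114, or 3.8%.
- Each percentage point of between-arm difference: 0.01 x 2 = 0.02 (6.7% of 0.3), or 0.01 x 4 = 0.04 (13.3%) for a death scored 5.
- Never-operated patient, per percentage point of extra non-operation in one arm: (0 - 1) x 0.01 = -0.01 if the patient scores 0, but (2 - 1) x 0.01 = +0.01 if worst-case quality of life applies and no event occurs. The sign depends on a rule that the plan does not state.

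**4. How much follow-up is involved.** Taking the 4-6 week programme as the wait, and T4 at 13 to 17.3 weeks:
- Time to T4: 4/(4 + 17.3) = 18.8% up to 6/(6 + 13) = 31.6%.
- Time to one year: 4/56 = 7.1% up to 6/58 = 10.3%.

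These are shares of time, not of events. They are approximate, because section 7.3 describes the elective wait as longer than five weeks.

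**5. Cost in noise of counting these events.** Assumption, because the documents give no rate: a share p has a preoperative death (score d) and a share p has an infarction or stroke (usual score plus 2, so mean 3). The rest have mean 1.0; SD is 0.9 in all but the deaths. The difference to detect stays at 0.3.

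Mean = pd + 3p + (1 - 2p). Variance = pd² + p(0.81 + 9) + (1 - 2p)(0.81 + 1) - mean².

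For p = 0.005 and d = 3: 0.045 + 0.04905 + 1.7919 - 1.02² = 0.8456, so SD = 0.92. The other rows follow in the same way.

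| p | d | SD | Power at 143 per arm | n per arm for 80% |
|---|---|---|---|---|
| 0.5% | 3 | 0.92 | 78.5% | 149 |
| 1% | 3 | 0.94 | 76.9% | 155 |
| 0.5% | 5 | 0.95 | 75.7% | 159 |
| 1% | 5 | 1.00 | 71.6% | 176 |

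**The case against.** **Death may already count.** Table 2 scores all-cause death without a start, deaths come from the municipal administration, intention to treat is stated three times and patients are not replaced. A preoperative death can fairly be read as scoring 3 already. This stands. A reader might infer that the plan drops such deaths, or excludes patients who are not operated; no text says either. What remains is that the opposite reading is equally open for death, that interventions carry an express start at the operation, and that infarction and stroke probably share it because their question follows directly.

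**The surgery anchor is the stated question.** The objective asks about outcome after the operation. This also stands: the anchor is not an error, and replacing it outright would change the question. It does not remove the need to say how a preoperative death or a never-operated patient is scored, whichever origin is chosen.

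**A window from randomisation to one year after surgery has its own flaw.** Its length varies with the wait, which follows randomisation and could differ by arm. That is correct, and the window end proposed below avoids it.

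**Events may be few.** Patients are elective, several comorbidities are excluded and a cycling test precedes entry. This is plausible, but the documents give no rate to confirm it.

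**Conclusion.** The point holds as a gap in the definition of the primary endpoint. For interventions the text as written excludes the preoperative interval. For infarction and stroke it probably does, for death it is ambiguous, and for patients never operated there is no assessment date. The primary comparison may thus be conditioned on reaching surgery, which conflicts with the stated intention to treat.

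The size and direction of any bias are unknown. A reader might infer that the result will favour one arm, or that many patients are affected; the documents support neither. What can be said is the leverage: 0.011 points per death (scored 3) or per infarction or stroke, and 0.02 points per percentage point of imbalance, against a target of 0.3. These figures rest on the planning mean of 1.0 and 175 per arm, and the figure for a death doubles if worst-case quality-of-life points are added. The stated sample size reproduces and is not in question. The change should be made because it protects the primary comparison and most of the data are already collected.

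**What to change.** 1. At T4 and T6, ask about interventions, infarction and stroke from randomisation onward.
2. In Table 2 and the screening text of section 2, state that death, infarction, stroke and non-index interventions count from randomisation. Treat the planned operation as the index operation whenever it takes place. Leave the in-hospital and day-30 readmission windows unchanged.
3. Keep every randomised patient in the analysis, with a nominal date (for example the planned surgery date) for those not operated.
4. State whether the worst-case quality-of-life points in section 9.1 apply to patients who die or are not operated.
5. Report this all-randomised score alongside the surgery-anchored score of section 1.1. End its window at a time that does not depend on the actual wait: a fixed time from randomisation or from the planned surgery date.
6. Report non-operation and waiting time by arm, and give the blinded endpoint committee the window in writing.

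**Cost.** AEs and SAEs are already asked at T2, hospital records are already checked and deaths are already traced. Never-operated patients need a few extra contacts, since T2 is itself tied to the operation: "The second measurement is one day before surgery (T2"). Preoperative admissions remain uncounted. Noise rises slightly: at the assumed 0.5-1% rates, power at 143 per arm is about 77-78.5% with a death scored 3, or about 72-76% with a death scored 5. To the extent that preoperative deaths would be scored anyway, that part of the cost is not new.
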